6.9.9 Disease Status

Number and percentage of subjects with a diagnosis of disease relapse (Yes/No) or cGVHD (Yes/No) as assessed at Study Days 253 and 337 will be presented by visit.

In addition to the safety population, this analysis will also be conducted using the evaluable population, the safety population for subjects with ≤ 3 day of systemic steroid dosing prior to dosing of study medication, and the safety population for subjects with > 3 day of systemic steroid dosing prior to dosing of study medication.

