Part B of the study will be randomized, double blinded, and placebo controlled, and will commence following the completion of Part A and approval by the DSMC. In Part B, approximately 60 subjects will be enrolled to better define the safety, tolerability, [REDACTED], and to explore the clinical activity of EQ001 in subjects with newly [REDACTED] [REDACTED] aGVHD.

[figure not shown]
After informed consent has been obtained, all subjects will be screened for potential participation, and those meeting eligibility criteria will be offered participation in the study. The study will enroll subjects with an initial clinical diagnosis of aGVHD requiring systemic immunosuppressive treatment. All subjects must receive their first dose of study drug within 72 hours (3 days) of the subject's initial systemically administered corticosteroid dose.

The systemically administered corticosteroid treatment will be prednisone, at approximately 1-2 mg/kg/day (or its equivalent) at the time of first dose of study drug administration; however, the investigator can adjust dosing as clinically indicated during the study according to the recommended treatment and tapering schedule [REDACTED]

Subjects in Parts A and B will have the same study assessments except as noted. All subjects will have two (2) months of dosing comprising five (5) doses of study drug, administered IV every fourteen (14) days, and ten (10) months of follow up for a total of twelve (12) months in the study. The follow-up period will consist of a 2-month Safety Follow-Up period (through Day 169) and then an 8-month Long-Term Follow-Up period (through Day 337). [REDACTED]

[REDACTED] overview of the study timeline for Part A and Part B, respectively. During the Long-Term Follow-Up period, the site will phone subjects on Study Days 253 and 337 to collect information on disease status (disease relapse or cGVHD), long-term survival, and safety (eg, recent hospitalization or SAEs).

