9.9. Efficacy Analyses

[REDACTED]

[REDACTED]

[REDACTED]

[REDACTED]

[REDACTED]

[REDACTED]

[REDACTED]

All efficacy data summaries for Part A will use the safety population, whereas Part B will use the efficacy population for Part B. Clinical activity will be assessed by change from baseline in: aGVHD Organ Stages and Overall Clinical Grading and aGVHD-AI. Corticosteroid and immunosuppressive agent usage will be compared between groups. Overall mortality and nonrelapse-mortality at 12 months, overall response rate (proportion of subjects with a best response of PR or better during the 12-month assessment period compared to last pre-dose assessment) and Kaplan-Meier estimates of progression-free survival will also be calculated. In general, changes from baseline in numeric variables will be compared between the two groups using an analysis of covariance model with baseline value as a covariate. Proportions will be compared between the groups using the Fisher's Exact test. Time to event data will be compared using the log-rank test.

[REDACTED]

[REDACTED]

[REDACTED]

[REDACTED]

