3.1 Clinical Activity Endpoints

- Response to therapy (Complete response [CR], Very Good Partial Response [VGPR], Partial response [PR], No response [NR], and Progressive disease [PD])
- Progression-free survival (PFS)

Statistical Analysis Plan

Sponsor Name: Equillium Inc.

Sponsor Protocol ID: EQ001-aGVHD-001

- aGVHD activity index (aGVHD-AI) and change from baseline
- Organ stages and change from baseline
- aGVHD overall clinical grade and change from baseline
- Overall survival (OS) – Time from first dose to death from any cause
- Relapse incidence and non-relapse mortality
- Corticosteroid usage
- Subjects who discontinued corticosteroids
- Disease status (disease relapse or chronic GVHD (cGVHD)) during long-term follow-up period

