6.10.5 Relapse of Underlying Malignancy and Death

Number and percentage of subjects whose underlying malignancy relapsed or died will be summarized for the following categories:

- Malignancy relapsed by Day 29
- Death by Day 29
- Death by Day 29 with no relapse of malignancy
- Malignancy relapsed during the study
- Death during study with no relapse of malignancy
- Death during study after relapse of malignancy

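### Relapse incidence and non-relapse mortality are listed as endpoints, but the readable Part A SAP gives no cumulative-incidence estimate, and the Day 253/337 relapse table has no denominator or rule for deaths

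*SAP*

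**What the plan says.** SAP 3.1 includes "Relapse incidence and non-relapse mortality" among the clinical activity endpoints. Three readable displays bear on it.

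- **SAP 6.10.5:** "Number and percentage of subjects whose underlying malignancy relapsed or died will be summarized for the following categories". The whole-study categories include "Malignancy relapsed during the study", "Death during study with no relapse of malignancy" and "Death during study after relapse of malignancy". SAP 6.10 assigns safety summaries to the safety population, so the denominator is everyone dosed.
- **SAP 6.9.2:** relapse of the underlying malignancy is one of the PFS events, and events are tabulated by type.
- **SAP 6.9.9:** "Number and percentage of subjects with a diagnosis of disease relapse (Yes/No) or cGVHD (Yes/No) as assessed at Study Days 253 and 337", by visit. The table is repeated in the evaluable population and in two subgroups defined by length of prior steroid dosing. Protocol 3.1 gives the source of these data: "the site will phone subjects on Study Days 253 and 337 to collect information on disease status (disease relapse or cGVHD), long-term survival".

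Elsewhere the SAP plans Kaplan-Meier estimates for PFS, overall survival (OS), time to laboratory grade increase and, if data permit, chronic GVHD. No readable section gives a time-based estimator, censoring rule or confidence interval for relapse or NRM.

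**The concern.** Relapse is a central harm question when immunosuppression is added after transplant, and NRM is where benefit might show. Each precludes or alters the other, and follow-up will differ between subjects. A percentage of all dosed subjects ignores follow-up time: someone lost at Day 100 counts as free of both events through the end of the study.

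The 6.9.9 table has a separate problem. A subject who relapses and dies before Day 253 cannot be phoned, and the SAP does not say whether that subject counts as a yes, counts as a no, or drops out of the table. A reader could take the Day 337 row as one-year relapse incidence when it may be something quite different.

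**Working it through.** The documents state no relapse, NRM or loss rate, so there is no planned figure to reproduce. The rates below are assumptions. From the documents come the horizon (Day 337) and the Part A size (about 24, plus up to about 15, so up to about 39).

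**1. Crude percentage in 6.10.5.** Assume constant hazards and independent loss. Let R and M be the true cumulative incidences of relapse and NRM at T = 337 days, and q the proportion lost by T in the absence of events. Put H = −ln(1 − R − M) and K = −ln(1 − q). Then

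crude relapse = R/(R+M) × H/(H+K) × [1 − (1−R−M)(1−q)],

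and crude NRM is the same with M/(R+M) in front. With q = 0 this reduces to R, so crude percentage and cumulative incidence agree. In 4,000 simulated trials at each of n = 24 and n = 39 without loss, the crude and Aalen-Johansen values were identical in every trial.

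Take R = 25% and M = 20%, so H = 0.598. For q = 10%, K = 0.105 and crude relapse = 0.556 × 0.850 × (1 − 0.55 × 0.90) = 23.9%.

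| Loss | Relapse shown (true 25%) | NRM shown (true 20%) |
|---|---|---|
| 10% | 23.9% | 19.1% |
| 20% | 22.7% | 18.1% |
| 30% | 21.4% | 17.1% |

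The shortfall is 1.1 to 3.6 points for relapse and 0.9 to 2.9 for NRM. For comparison, the standard error of a 20% proportion is √(0.2 × 0.8/24) = 8.2 points at n = 24 and √(0.2 × 0.8/39) = 6.4 points at n = 39.

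**2. Day 337 row of 6.9.9.** Suppose only living subjects can contribute a yes. Let A = H × R/(R+M), and let C be the cumulative death hazard after relapse over 337 days (0.693 × 337/median). The proportion relapsed and alive is A × (e^−H − e^−C)/(C − H). The proportion alive is e^−H plus that. For R = 25%, M = 20% and a 60-day median, A = 0.332 and C = 3.893. This gives 0.332 × (0.550 − 0.020)/3.295 = 5.3% of those dosed, and 5.3/(55.0 + 5.3) = 8.8% of those alive.

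| True relapse / NRM | Survival after relapse | Yes / all dosed | Yes / alive |
|---|---|---|---|
| 25% / 20% | median 60 days | 5.3% | 8.8% |
| 25% / 20% | median 120 days | 10.0% | 15.4% |
| 25% / 20% | median 365 days | 17.9% | 24.5% |
| 25% / 20% | median 400 days | 18.4% | 25.1% |
| 30% / 30% | 30% die within 168 days | 20.3% | 33.7% |

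With survivors as denominator, the row runs from far below the true incidence to above it (33.7% against 30%). With all dosed as denominator and only living subjects able to give a yes, it is low in every row. The SAP does not say which denominator applies.

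**3. NRM classification.** Protocol section 7 collects adverse events to Day 169 for subjects who complete dosing and to Day 85 for those who stop early, but deaths to Day 337 unless consent is withdrawn. If a late death is reported and an earlier relapse is not, 6.10.5 counts it as death without relapse. That raises NRM, the opposite direction from loss to follow-up.

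**The case against.** A reader might infer that relapse is necessarily understated because the dead cannot answer the calls. The documents do not support that. 6.10.5 counts relapse at any time and separately counts deaths after relapse, and 6.9.2 takes relapse as a PFS event. The subject missing from 6.9.9 can therefore still be counted elsewhere. Competing deaths do not bias the crude percentage; incomplete follow-up does. The large gaps in the 6.9.9 rows depend on an unstated denominator and on assumed short survival after relapse, and they can vanish or reverse. Nor do all errors run toward fewer events, because 6.9.9 does not report NRM and a missed relapse before death would inflate it.

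A reader might also infer that Part B will test NRM with Fisher's exact test. Protocol 9.9 lists "Overall mortality and nonrelapse-mortality at 12 months" among quantities to be calculated. It then assigns Fisher's test to proportions and the log-rank test to time-to-event data, without saying which class NRM falls in. The surrounding text is redacted and the readable SAP covers Part A, so the Part B method cannot be judged.

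Two further points stand. Part A is small and descriptive, so a 1 to 4 point correction lies within sampling error. SAP section 5 and parts of protocol section 9 are not visible, so a definition there cannot be excluded.

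None of this supplies an estimator for a listed endpoint or a denominator for 6.9.9. The PFS breakdown does not fill the gap: PFS takes the earliest event, so a relapse after GVHD progression is not in its relapse row.

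**Conclusion.** The point holds in limited form. In the readable Part A SAP, relapse incidence and NRM have no estimator that accounts for follow-up time. The 6.10.5 percentage is right with complete follow-up and about 1 to 4 points low with 10-30% loss, assuming true rates of 20-25%, constant hazards and independent loss. The 6.9.9 table is not interpretable as relapse incidence until its denominator and its rule for earlier deaths are stated, and the direction of its error is not fixed. It also refers to disease relapse without tying the term to the underlying malignancy, as 6.9.2 and 6.10.5 do. The consequence for Part A is modest. The change is still worth making, because relapse and NRM bear on harm and benefit and the remedy is cheap.

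**What to change.** - **6.10.5:** in the safety population, add Aalen-Johansen cumulative incidence of relapse and of NRM from first dose, each as the competing event of the other, censored at last contact. Give confidence intervals at Days 29, 169 and 337, and state their level. Keep the existing counts as support.
- **Data source:** take the relapse date, and relapse status at death, from all relapse and death reports, not only the two calls.
- **6.9.9:** either count relapse cumulatively to each visit over all dosed subjects, or label the table as status among subjects contacted and show how many were contacted, dead or lost. Say whether disease relapse means the underlying malignancy.

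Relapse dates are already needed for PFS and last-known-alive dates for OS, so the cost is mainly SAP wording and one standard procedure. The downsides are a little more analysis work, wide intervals with about 24 to 39 subjects, and possibly slightly higher reported rates.

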6.10 Safety

All safety data summaries will use the safety population. Safety analyses will be presented by cohort and overall unless otherwise specified.

Number and percent of subjects experiencing any DLTs will be presented by cohort. A listing of DLTs will also be provided.

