9.7. Safety Analysis

All safety data summaries will use the safety population.

For subjects in Part A, number and percent of subjects experiencing any DLTs will be presented by cohort. A listing of DLTs will also be provided.

AEs will be coded using the Medical Dictionary for Regulatory Activities (MedDRA) and will be graded by the investigator using the CTCAE v5.0 or the current version. Subject incidence of TEAEs, treatment-emergent serious AEs (TESAEs), TEAEs leading to treatment discontinuation and TEAEs with an outcome of death will be summarized by SOC and preferred term (PT). AEs will also be further summarized by worst severity grade and relationship to study drug. [REDACTED]

[REDACTED]

[REDACTED]

Clinical laboratory data will be summarized descriptively, these summaries will include observed values at collection timepoints and change from baseline. All laboratory parameters that can be graded using the CTCAE will be graded. [REDACTED]

[REDACTED]

[REDACTED]

[REDACTED]

[REDACTED]

[REDACTED]

[REDACTED]

[REDACTED]

[REDACTED]

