Subjects will be considered evaluable for DLT assessment if they have received at least two doses of study drug and completed through Study Day 29 assessments or received at least one dose of study drug and had a DLT within the DLT window. During the DLT assessment window, subjects who do not complete the specified study procedures or withdraw from the study for reasons other than a DLT may be replaced. Replaced subjects will receive the same dose level and cohort assignment as the subject they are replacing.

Established Data and Safety Monitoring Committee (DSMC) will apply the following dose escalation rules based on the subject incidence of DLTs:

- If 0 of the 3 initial evaluable subjects experiences a DLT, then escalation may proceed to the next highest dose level.

[figure not shown]
Statistical Analysis Plan

Sponsor Name: Equillium Inc.

Sponsor Protocol ID: EQ001-aGVHD-001

- If 1 of the 3 initial evaluable subjects experiences a DLT, then 3 additional subjects will be enrolled at the same dose level for a total of up to 6 evaluable subjects.
 - If 1 out of the 6 subjects experience a DLT, then escalation may proceed to the next higher dose level.
 - If 2 or more out of the 6 subjects experience a DLT, escalation to the next dose level will not proceed, next lower dose level will enroll additional subjects for a total of 6 evaluable subjects.
- If 2 of the 3 initial evaluable subjects experience DLTs, escalation to the next dose level will not proceed, next lower dose level will enroll additional subjects for a total of 6 evaluable subjects.

Enrollment of the next higher dose cohort will not commence until all safety data from all subjects from prior cohorts and all available safety data from the current cohort through Study Day 29 have been reviewed by the DSMC and approval is granted for dose escalation.

3. Clinical Activity and Safety Variables for Part A

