4.1 Safety Population

Safety population consists of all subjects who receive any study medication. All data summaries except PK and PD data related summaries will use this population.

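### The DLT percentage by cohort is taken over all treated subjects, while the 3+3 rule counts DLT-evaluable subjects, so it is diluted in a cohort that has both a DLT and a treated non-evaluable subject

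*SAP*

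**What the plan says.** On reporting, SAP 6.10 opens with "All safety data summaries will use the safety population". It then says "Number and percent of subjects experiencing any DLTs will be presented by cohort", adds a DLT listing, and names no other denominator. Protocol 9.7 has the same general rule and the same output: "For subjects in Part A, number and percent of subjects experiencing any DLTs will be presented by cohort". SAP 4.1 defines the denominator: "Safety population consists of all subjects who receive any study medication". SAP 6.10.1 also plans an overview row for any DLT adverse event and a table of DLT adverse events by system organ class and preferred term. Both fall under the same general rule.

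On escalation, SAP 2.2 uses a narrower group. There are two routes into it. The first is "Subjects will be considered evaluable for DLT assessment if they have received at least two doses of study drug", together with completion of the Day 29 assessments. The second is to have "received at least one dose of study drug and had a DLT within the DLT window". The rule is worded on that group, for example "If 1 of the 3 initial evaluable subjects experiences a DLT, then 3 additional subjects will be enrolled at the same dose level". The same section foresees treated subjects who do not qualify: "subjects who do not complete the specified study procedures or withdraw from the study for reasons other than a DLT may be replaced".

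SAP 4.2 defines a separate evaluable population that requires at least two doses. Its stated use is selected analyses of response, relapse and survival.

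**The concern.** The DLT percentage by cohort is the summary that a reader will set beside the escalation record, and the two do not share a denominator. A subject who had one dose, left for a reason other than toxicity and was replaced does not count for the rule, but stays in the safety population and so in the denominator of the percentage. Such a subject was not observed through the DLT window, yet is treated in the table as someone who passed through it without a DLT.

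Safety, tolerability and choice of dose are the primary objectives of Part A, and this percentage is a direct output for them. At stake is whether the table shows the DLT rate among the 3 or 6 subjects behind each decision, or a somewhat lower figure.

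**Working it through.** The documents state no DLT percentage, so there is no figure of the plan's own to reproduce. The check is direct arithmetic.

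**Inputs**
- x: subjects in the cohort with a DLT.
- n: DLT-evaluable subjects, 3 or 6 under the rule in SAP 2.2.
- k: treated subjects who are not DLT-evaluable. The documents give no rate, so k is an assumption. It is shown from 0 up to 25% of treated subjects, which means k = 0, 1 or 2 when n = 6, and k = 0 or 1 when n = 3.

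**Step 1: the numerator.** Protocol 3.2.1 confines DLTs to Study Days 1 to 29 of the dose escalation. Under the second route in SAP 2.2, any dosed subject with a DLT in that window is evaluable. Every subject with a DLT is therefore in both sets, and x is the same on both bases.

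**Step 2: the denominators.** Rate over evaluable subjects: x/n. Reported rate over the safety population: x/(n + k). The second is lower exactly when x ≥ 1 and k ≥ 1. If x = 0, both are 0%. If k = 0, they are identical.

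**Step 3: the size.** The relative understatement is 1 − [x/(n + k)]/[x/n] = k/(n + k). Gaps below are taken before rounding.

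| DLTs / evaluable | Evaluable rate | k = 1 | k = 2 | Gap at k = 1 | Gap at k = 2 |
|---|---|---|---|---|---|
| 1/6 | 16.7% | 1/7 = 14.3% | 1/8 = 12.5% | 2.4 points | 4.2 points |
| 2/6 | 33.3% | 2/7 = 28.6% | 2/8 = 25.0% | 4.8 points | 8.3 points |
| 2/3 | 66.7% | 2/4 = 50.0% | beyond the range | 16.7 points | – |

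The relative understatement is 1/7 = 14.3% for one subject added to six, 2/8 = 25.0% for two added to six, and 1/4 = 25.0% for one added to three. One DLT in three is left out because the rule then takes the cohort on to six.

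**Step 4: whether the SAP 4.2 population would serve instead.** It would not. It requires at least two doses, and the protocol synopsis (dose modification) and protocol 3.2.2 stop dosing at a DLT. A subject with a DLT after the first dose would leave both the numerator and the denominator.

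**The case against.** The strongest reply is that DLTs over all treated subjects is a defined and disclosed summary. The SAP names and defines its population, the protocol agrees with it, and neither document promises a DLT rate over evaluable subjects. On this view evaluability is a counting device for the monitoring committee, and preferring it for the table is a matter of taste.

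Much of this stands:
- The committee applies the rule to counts of evaluable subjects, so the table changes no decision.
- The DLT count and listing remain. SAP 6.6 gives the number of doses received, SAP 6.2 gives discontinuations by reason, and protocol 9.1 promises by-subject listings. In cohorts of 3 to 6, a reader could largely work out who was evaluable.
- The size depends on an assumed k. The largest gap, at 2/3, falls where escalation has already stopped. In the 1/6 case, which still allows escalation, one added subject moves 16.7% to 14.3%, while the exact 95% intervals are 0.4% to 64.1% and 0.4% to 57.9%.

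The reply does not remove the point. The plan ties DLT assessment to a stated evaluability definition and expects some treated subjects to fall outside it. The visible reporting rule then divides by a group that includes them. When the two rates differ, the difference always runs towards a lower DLT rate, and the table itself gives no sign of it. Safety-population reporting remains proper for the general adverse event tables.

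A reader might also infer that the SAP lacks a DLT-evaluable set altogether. That cannot be established. Text after SAP 4.3 and around protocol 9.3.3 is not visible, and SAP section 1 places table specifications in a separate document.

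**Conclusion.** The point holds on the visible text as a modest reporting fault that should be corrected. The reported percentage falls below the evaluable rate only when a cohort has at least one DLT and at least one treated non-evaluable subject. Within the assumed range, the gap is 2.4 to 8.3 percentage points with six evaluable subjects, and 16.7 points for two DLTs in three. It rests on two assumptions: the value of k, and that no unseen section or table specification assigns another denominator. No claim is made about how often such a cohort will arise.

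Three stronger readings are not supported:
- **That escalation is biased.** The rule uses counts of evaluable subjects, not this percentage.
- **That DLTs will be computed on the SAP 4.2 population and some lost.** Nothing visible applies that population to DLTs. It matters only as a set to avoid when making the correction.
- **That the up to approximately 15 additional subjects at the selected dose will dilute the percentage further.** The documents do not say that they share a column with the escalation cohort, and protocol 3.2.1 defines DLTs only during the 3+3 escalation.

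**What to change.** In SAP section 4, define a DLT-evaluable set using the two routes in SAP 2.2. Limit it to subjects enrolled in the 3+3 escalation and counted for the escalation decisions. The additional subjects at the selected dose (protocol 3.1) and any further subjects approved by the monitoring committee (protocol 3.2) then do not enlarge the denominator. Do not use the SAP 4.2 population.

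In SAP 6.10, report DLT n/N and % by cohort over this set, with the number treated beside it. In SAP 6.10.1, footnote the DLT overview row and the DLT table by system organ class and preferred term as based on the safety population, so that the two percentages can be reconciled. If unseen text or the table specifications already do this, add a cross-reference in SAP 6.10 instead.

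The cost is one analysis flag, a short piece of SAP wording and two footnotes. Two DLT denominators will appear in the report, and the DLT percentages may look slightly less favourable.
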